8.3.3 CLASSIFICATION OF AN ADVERSE EVENT

8.3.3.1 SEVERITY OF EVENT

As part of the safety monitoring system, AEs reported to study staff at any time will be reviewed by the medical safety officer, who will identify, assess severity and relatedness to study drug, and if needed, manage the event. The study staff will report AEs and/or any unanticipated problems, to the medical safety officer. For AEs that require medical attention, the medical safety officer will directly contact the subject.

Safety related events will be reported within 10 days, as required by the SMC and the IRB that are responsible for study oversight.

For ongoing participant safety, events are assessed by the medical safety officer or Investigator to determine if they are Serious, Unexpected, or Related to study participation. If the event is reportable to the IRB, an event evaluation form will be completed that will include a description of the event, a classification of seriousness, assessment of potential relationship to the intervention, assessment of need for change in the consent or the study activities, a summary of known prior health issues, event outcome and a classification of the main organ system involved. The classification of potential relationship to the intervention is as follows.

Definite - Temporal pattern + Known or expected AE response pattern + Confirmed by stopping the intervention + Reappearance of AE on re-challenge

Probable - Temporal pattern + Known or expected AE response pattern + Confirmed by stopping the intervention + could not be explained by participant's clinical state

Possible - Temporal pattern + Known or expected AE response pattern + could have been produced by a number of other factors

Unknown - Relationship for which no evaluation can be made.

Not related - AE for which sufficient information exists to indicate that the cause is unrelated to the study intervention

The medical safety officer or the Investigator will determine the attribution/relatedness of each AE. The PI will report AEs to NINR every 6 months, including actions taken by the IRB as a result of such AEs.

See MOP chapter 12, Safety Monitoring and Serious Adverse Events, for more details of adverse and serious adverse events (SAEs) including the Study Medication Symptom Monitoring Form, the Adverse Event Form, and the Suicide Algorithm.

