8.3.3.3 EXPECTEDNESS

The medical monitor or Investigator will be responsible for determining whether an AE is expected or unexpected. An AE will be considered unexpected if the nature, severity, or frequency of the event is not consistent with the risk information previously described for the study procedures.

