8.4 UNANTICIPATED PROBLEMS

8.4.1 DEFINITION OF UNANTICIPATED PROBLEMS

An unanticipated problem is any event, incident, experience, or outcome (including, but not limited to, adverse events and serious adverse events) which occurs in a research study and **meets ALL** of the following criteria:

- Unexpected in nature, frequency, or severity (not articulated in the study protocol, informed consent or Investigator's Brochure or not expected as a consequence of the natural history of a disease under study)
- Related or possibly related to participation in the research (there is a reasonable possibility that the event, incident, experience, or outcome may have been caused by the drug/device, procedures or interventions involved in the research)
- Places subjects or others at a greater risk of harm than was previously known or recognized (causes physical, psychological, economic, or social harm to a human subject; increases the risk of harm of any kind; or otherwise compromises subject's safety, rights, welfare, or privacy).

Reportable events are not limited to physical injury, but also include psychological, economic, and social harm. Reportable events may arise as a result of the use of drugs, biological agents, devices, procedures or other interventions, or as a result of the use of questionnaires, surveys, observations or other interactions with research subjects. All breaches of confidentiality are reportable events. Reporting to the IRB is required regardless of the funding source or study sponsor.

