8.4.2 UNANTICIPATED PROBLEMS REPORTING

The investigator will report unanticipated problems (UPs) to the reviewing IRB and to the Data Coordinating Center (DCC). The UP report will include the following information:

- Protocol identifying information: protocol title and number, PI's name, and the IRB project number
- A detailed description of the event, incident, experience, or outcome
- An explanation of the basis for determining that the event, incident, experience, or outcome represents an UP
- A description of any changes to the protocol or other corrective actions that have been taken or are proposed in response to the UP

To satisfy the requirement for prompt reporting, UPs will be reported using the following timeline:

- UPs that are SAEs will be reported to the IRB, the DCC, and the NINR Program Officer within 48 hours of the investigator becoming aware of the event
- Any other UP will be reported to the IRB, the DCC, and the NINR Program Officer within 7 calendar days of the investigator becoming aware of the problem
- All UPs should be reported to appropriate institutional officials (as required by an institution's written reporting procedures) and the supporting agency head (or designee)
- OHRP reporting is made by the IRB in accordance with federal and institutional requirements

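### The causality scale in 8.3.3.1 bars a new kind of adverse event from every related category, while 8.4.1 applies a broader relatedness test, and the protocol does not say which governs

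*Combined protocol and SAP*

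**What the plan says.** Section 8.3.3.1 lists five relationship categories, with the conditions of the top three joined by plus signs:

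- The strongest rating is worded "Definite - Temporal pattern + Known or expected AE response pattern + Confirmed by stopping the intervention + Reappearance of AE on re-challenge".
- The next one down begins "Probable - Temporal pattern + Known or expected AE response pattern + Confirmed by stopping the intervention" and adds a further condition, that the participant's clinical state does not explain the event.
- The weakest rating that still asserts a relationship is worded "Possible - Temporal pattern + Known or expected AE response pattern + could have been produced by a number of other factors".
- The fourth makes no claim either way: "Unknown - Relationship for which no evaluation can be made".
- The fifth, Not related, needs enough information to show that the cause lies elsewhere.

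Section 8.3.3.2, the section titled for relationship to the intervention, only refers back to this list. Section 8.3.3.1 has the medical safety officer or investigator settle relatedness for each AE, and 8.3.4 has relationship recorded for AEs generally.

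Expectedness is judged separately in 8.3.3.3: "An AE will be considered unexpected if the nature, severity, or frequency of the event is not consistent with the risk information previously described".

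Section 8.4.1 requires a UP to meet three criteria together. The first is "Unexpected in nature, frequency, or severity". The second is "Related or possibly related to participation in the research", which the text explains as a reasonable possibility that the drug, procedures or interventions caused the event. The third is a greater risk of harm than was previously recognised. Under 8.4.2, "UPs that are SAEs will be reported to the IRB, the DCC, and the NINR Program Officer within 48 hours"; other UPs go to the same three recipients within 7 calendar days.

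**The concern.** UP reporting is meant to catch harm that is both unexpected and possibly caused by the study. The scale in 8.3.3.1 works least well for exactly that class. It makes a known or expected pattern a condition of causality, so a judgement about expectedness, which 8.3.3.3 already covers, also decides how high the causality rating can go. A new kind of event with a clear temporal pattern, which resolves when the intervention stops, still cannot be rated even Possible.

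Section 8.4.1 asks a different question and can give the opposite answer for the same event. The trial adds a web-based programme, with or without telephone support, to a drug, so a harm that no one has described beforehand is a case the safety rules should handle cleanly. At stake are the expedited notice to the IRB, the DCC and the NINR Program Officer, and the consistency of the safety record.

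**Working it through.** No sample size, power or event rate bears on this point, and the plan states no figure to reproduce. The check sets the two rules side by side for one test case: an AE that is new in nature, has a clear temporal link to the intervention and has no evident other cause.

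**Step 1. The scale in 8.3.3.1, read literally.**

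| Category | Asserts a relationship? | Known or expected pattern required? | Open to the test case? |
|---|---|---|---|
| Definite | Yes | Yes | No |
| Probable | Yes | Yes | No |
| Possible | Yes | Yes | No |
| Unknown | No | No | Yes |
| Not related | No (denies one) | No | Only with evidence of another cause |

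Three of the five categories assert a relationship, and 3 of those 3 require the pattern. That leaves 0 of 3 related categories and 5 − 3 = 2 others. Without evidence of another cause, the rating is Unknown.

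**Step 2. The UP definition in 8.4.1.**

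- Criterion 1 (unexpected): met, because the event is new in nature.
- Criterion 2 (related or possibly related): can be met. The test is a reasonable possibility of causation. It has no pattern condition, does not cite the 8.3.3.1 scale, and concerns participation in the research rather than the intervention alone.
- Criterion 3 (greater risk than recognised): depends on the event.

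So the same event can be Unknown under 8.3.3.1 and possibly related under 8.4.1.

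**Step 3. What follows when no rule of precedence is given.**

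- If staff answer criterion 2 with the scale rating, Unknown is neither related nor possibly related. All three criteria must hold, so the event is not classed as a UP, and the 48-hour or 7-day notice in 8.4.2 does not apply.
- If staff answer criterion 2 with the 8.4.1 test, the event can be reported as a UP. Section 8.4.2 then asks the report to explain the basis for that determination, while the event evaluation form shows Unknown.

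**Step 4. Which events are affected.** An AE unexpected only in frequency or severity can still follow a known pattern, so it can be rated related on the scale and meet 8.4.1. The conflict is confined to events unexpected in nature.

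**The case against.** The strongest reply is that the scale does not decide UP status. Section 8.4.1 carries its own relatedness test and never cites the scale. Section 8.3.3.1 also has events judged serious, unexpected or related first, and describes the event evaluation form as completed once an event is reportable to the IRB. This stands, and it rules out one tempting reading. A reader might infer that a novel AE cannot meet the UP definition at all; the documents do not support that, because the event is blocked only if staff use the scale to answer criterion 2, which no section tells them to do. The reply does not remove the inconsistency. The first triage already asks about relatedness, the scale is the only graded tool offered for it, and 8.3.3.2 sends the reader straight to it.

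A reader might also infer that a missed event would wait up to about six months for the next twice-yearly SMC meeting. That is not supported. Under 8.2, AEs found by symptom monitoring go to the medical safety officer, and the study team reviews serious and unexpected AEs monthly. Section 8.3.3.1 has a 10-day route and 8.3.6 a 10-working-day route for events meeting IRB criteria. Section 10.1.6 lets the SMC ask for information at any time.

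Nor do the documents show that SMC or NINR reports would undercount related events. Sections 8.3.3.1 and 10.1.6 describe AE reports that are not limited to related events, and neither says that they are split by relatedness. The re-challenge condition in Definite does not matter here, since possibly related is enough under 8.4.1.

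Finally, known or expected pattern is not the exact opposite of unexpected. Unexpectedness is judged against the study's described risks, and a pattern could be known from elsewhere, such as the pharmacology of the drug class. The protocol does not define the phrase that way, but the reply is fair: the exclusion in Step 1 is a literal reading, not the only possible one.

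**Conclusion.** The protocol contains two relatedness standards that can give opposite answers for an AE that is new in nature, and no rule says which one governs. On the literal reading, all 3 related categories of the 5-category scale are closed to such an event, including the lowest. The supportable consequence is a possible loss of the 48-hour or 7-day notice if the scale rating is carried into UP criterion 2, or otherwise a conflict between the event form and the UP report. The reporting pathway itself is not closed, and other review routes remain.

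The conclusion rests on two assumptions: that an event new in nature has no known or expected pattern, and that Manual of Procedures chapter 12, which is cited for detail but is not among the documents, does not already resolve the matter. Even if it does, 8.3.3.1 and 8.4.1 should agree. The number of events affected cannot be estimated from the documents and may be small. The wording should be corrected.

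**What to change.** Reconcile 8.3.3.1 to 8.3.3.3 with 8.4.1:

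1. Define Possible in 8.3.3.1 by the reasonable-possibility test of 8.4.1, and delete the pattern condition from it.
2. In Definite and Probable, treat a known or expected pattern as supporting evidence rather than a required element.
3. State that the 8.4.1 test governs the UP decision, and that a rating of Unknown does not rule out possibly related.
4. Leave expectedness to 8.3.3.3 alone.
5. Bring the event evaluation form, and Manual of Procedures chapter 12 where needed, into line.

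This is a short wording amendment with a matching form change. It alters no endpoint, analysis or sample size. The price is that a few more events will be rated Possible and reported.

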8.3.3.2 RELATIONSHIP TO STUDY INTERVENTION/EXPERIMENTAL MANIPULATION

See section 8.3.3.1 above for classification of potential relationship to the intervention.

8.3.3.3 EXPECTEDNESS

The medical monitor or Investigator will be responsible for determining whether an AE is expected or unexpected. An AE will be considered unexpected if the nature, severity, or frequency of the event is not consistent with the risk information previously described for the study procedures.

8.3.4 TIME PERIOD AND FREQUENCY FOR EVENT ASSESSMENT AND FOLLOW-UP

The occurrence of an AE or SAE may come to the attention of study personnel during study visits and interviews of a study participant presenting for medical care.

All AEs, not otherwise precluded per the protocol, will be captured on the AE Form (included in MOP chapter 12, Safety Monitoring and Serious Adverse Events). Information to be collected includes event description, time of onset, clinician's assessment of severity, relationship to study procedures, and time of resolution/stabilization of the event. All AEs occurring while on study will be documented appropriately regardless of relationship. All AEs will be followed to adequate resolution or stabilization.

Any medical or psychiatric condition that is present at the time that the participant is screened will be considered as baseline and not reported as an AE. However, if the study participant's condition deteriorates at any time during the study, it will be recorded as an AE.

Changes in the severity of an AE will be documented to allow an assessment of the duration of the event at each level of severity to be performed. Documentation of onset and duration of each episode will be maintained for AEs characterized as intermittent.

Clinic staff and the study safety officer will record events with start dates occurring any time after informed consent is obtained. At each study visit, the investigator will inquire about the occurrence of AE/SAEs since the last visit. Events will be followed for outcome information until resolution or stabilization.

8.3.5 ADVERSE EVENT REPORTING

See section 8.3.3.1 above and MOP chapter 12, Safety Monitoring and Serious Adverse Events, for additional information on AE reporting.

8.3.6 SERIOUS ADVERSE EVENT REPORTING

In consultation with the PI, study team members will be responsible for reporting AEs, SAEs and unanticipated events that meet IRB reporting criteria, as soon as possible, but no later than 10 working days after the investigator first learns of the event.

8.3.7 REPORTING EVENTS TO PARTICIPANTS

N/A

8.3.8 EVENTS OF SPECIAL INTEREST

N/A

8.3.9 REPORTING OF PREGNANCY

See section 8.2 Safety Assessments for pregnancy related policy.

8.4 UNANTICIPATED PROBLEMS

8.4.1 DEFINITION OF UNANTICIPATED PROBLEMS

An unanticipated problem is any event, incident, experience, or outcome (including, but not limited to, adverse events and serious adverse events) which occurs in a research study and **meets ALL** of the following criteria:

- Unexpected in nature, frequency, or severity (not articulated in the study protocol, informed consent or Investigator's Brochure or not expected as a consequence of the natural history of a disease under study)
- Related or possibly related to participation in the research (there is a reasonable possibility that the event, incident, experience, or outcome may have been caused by the drug/device, procedures or interventions involved in the research)
- Places subjects or others at a greater risk of harm than was previously known or recognized (causes physical, psychological, economic, or social harm to a human subject; increases the risk of harm of any kind; or otherwise compromises subject's safety, rights, welfare, or privacy).

Reportable events are not limited to physical injury, but also include psychological, economic, and social harm. Reportable events may arise as a result of the use of drugs, biological agents, devices, procedures or other interventions, or as a result of the use of questionnaires, surveys, observations or other interactions with research subjects. All breaches of confidentiality are reportable events. Reporting to the IRB is required regardless of the funding source or study sponsor.

8.4.2 UNANTICIPATED PROBLEMS REPORTING

The investigator will report unanticipated problems (UPs) to the reviewing IRB and to the Data Coordinating Center (DCC). The UP report will include the following information:

- Protocol identifying information: protocol title and number, PI's name, and the IRB project number
- A detailed description of the event, incident, experience, or outcome
- An explanation of the basis for determining that the event, incident, experience, or outcome represents an UP
- A description of any changes to the protocol or other corrective actions that have been taken or are proposed in response to the UP

To satisfy the requirement for prompt reporting, UPs will be reported using the following timeline:

- UPs that are SAEs will be reported to the IRB, the DCC, and the NINR Program Officer within 48 hours of the investigator becoming aware of the event
- Any other UP will be reported to the IRB, the DCC, and the NINR Program Officer within 7 calendar days of the investigator becoming aware of the problem
- All UPs should be reported to appropriate institutional officials (as required by an institution's written reporting procedures) and the supporting agency head (or designee)
- OHRP reporting is made by the IRB in accordance with federal and institutional requirements

8.4.3 REPORTING UNANTICIPATED PROBLEMS TO PARTICIPANTS

Any unanticipated problem resulting in a change to the protocol that might affect participant's participation in the study will be reported to the participant should the IRB require this and the IRB will make the decision if re-consenting is needed.

9 STATISTICAL CONSIDERATIONS

9.1 STATISTICAL HYPOTHESES

We have two primary hypotheses (H1 and H2):

H1: Combination treatment with and without health care professional support is more effective than duloxetine monotherapy in improving BPI GPS.

The primary comparison will be the combination treated groups (with and without health care professional support) vs. duloxetine group.

H2: Combination treatment with health care professional support is more effective than combination treatment without health care professional support in improving BPI GPS.

The primary comparison will be combination group with health care professional support vs. without health care professional group.

Exploratory hypothesis: Compared to those without comorbid psychological distress, participants with comorbid psychological distress are more likely to respond to combination therapy (with and without health care professional support) than to duloxetine monotherapy.

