4.2 SCIENTIFIC RATIONALE FOR STUDY DESIGN

We initially thought of a 3-arm study that compares combination treatment [duloxetine and web-based CBT] vs. duloxetine only vs. web-based CBT only. Such a design would allow us to also compare drug vs. web based CBT. We discarded the idea because it would be unethical to randomize participants with coexisting depression to a treatment arm (i.e., web-based CBT alone) without targeted treatment for depression. In addition, given the general tendency for practicing clinicians to prescribe medication, a more clinically relevant question would be, "What is the additional benefits of web-based CBT when offered concurrently with duloxetine?" Alternatively, a 2-arm RCT (duloxetine only vs. web-based CBT) would be a reasonable design, with combination treatment reserved for those who are non-responders to either duloxetine or CBT alone. However, we rejected this alternative for two reasons: (1) our primary goal is to optimize treatment outcome and a single agent would only yield minimal pain relief; and (2) initiating CBT earlier during treatment may prevent disability and further pain chronicity.

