9.2 SAMPLE SIZE DETERMINATION

With 280 participants and 20% loss to follow-up, we will have 75 evaluable participants in each treatment group. Based on published literature (*Kroenke K et. al JAMA July 2014*), the estimated standard deviation (SD) for BPI GPS score is 2.2. Assuming a moderate correlation of 0.5 between baseline and follow-up measures, we estimate that the SD in an analysis of covariance (ANCOVA) will be approximately 1.9. Therefore, we will have 90% power to detect a difference of -1 in BPI GPS score between combination groups (n= 150) and drug only group (n=75) for Aim 1. The power will be 83% power for comparison between combination with health care professional (n=75) and combination without health care professional (n=75) for Aim 2. All power calculations are based on two-sided t tests with alpha level of 0.025 to adjust for Bonferroni correction of testing two main hypotheses.

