9.4.2 ANALYSIS OF THE PRIMARY ENDPOINT(S)

Primary Outcome

The primary outcome of the study is BPI GPS score collected at Weeks 13 and 25. BPI GPS is a self-report measure of pain severity and interference with proven reliability and validity across different pain conditions. The overall score is defined as the average of 11 items. Two subscales are also defined: BPI pain severity and BPI pain interference. BPI pain severity is the average of 4 items asking about current pain and worse, least, and average pain in the past week. BPI pain interference is the average of 7 items that rate how pain interferes with various activities (higher score indicate greater pain interference). All study participants will be analyzed according to randomized treatment assignment regardless of adherence to the treatment protocols. We have two primary hypotheses (H1 and H2):

H1: Combination treatment with and without health care professional support is more effective than duloxetine monotherapy in improving BPI GPS.

H2: Combination treatment with health care professional support is more effective than combination treatment without health care professional support in improving BPI GPS.

Research has shown that the use of ANCOVA with baseline measure as a covariate is an optimal method in both design and analysis of trials with a continuous primary outcome. Compared to the use of change score as the primary outcome, ANCOVA is generally superior in terms of efficiency, precision, and power. Therefore, the primary analysis will be Week 13 and 25 BPI scores as a primary outcome while adjusting for baseline measurement.

In primary analysis, we will fit a LMM to account for the correlation among the repeated measures. The model will include indicator variables for intervention arms, visit, and the interaction term. Covariates will include the pre-randomized measure of BPI global score, the stratification factor opioid use, and the number of pain sites. Average follow-up BPI global pain scores for the 3 intervention groups will be estimated using least square means. Two different contrasts will be constructed to test H1 and H2 separately, each at the significance level of 0.025.

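### H1 is tested only as the average of the two combination arms, so its success does not show that unsupported web-based CBT adds to duloxetine; a gated arm-level test would close the gap at no alpha cost

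*Combined protocol and SAP*

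**What the plan says.** The hypothesis appears in Sections 2.1, 3, 9.1 and 9.4.2. In Section 9.1 it reads "H1: Combination treatment with and without health care professional support is more effective than duloxetine monotherapy in improving BPI GPS". The next sentence there makes it operational: "The primary comparison will be the combination treated groups (with and without health care professional support) vs. duloxetine group". For H2, the same section says "The primary comparison will be combination group with health care professional support vs. without health care professional group".

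Section 9.2 powers H1 as 150 versus 75 and H2 as 75 versus 75, for a difference of −1. It splits the error between them: "All power calculations are based on two-sided t tests with alpha level of 0.025 to adjust for Bonferroni correction of testing two main hypotheses". Section 9.4.2 closes the list of confirmatory tests: "Two different contrasts will be constructed to test H1 and H2 separately, each at the significance level of 0.025". It also plans least square means for all three arms, as estimates. No section plans a test of either combination arm alone against duloxetine on the primary outcome.

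Section 4.2, explaining why a CBT-only arm was dropped, gives as the more clinically relevant question "What is the additional benefits of web-based CBT when offered concurrently with duloxetine".

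**The concern.** The only randomised comparison that isolates what web-based CBT adds to duloxetine is the unsupported combination arm against duloxetine alone. The pooled contrast averages that effect with the effect of CBT plus six motivational interviewing calls. H1's wording can be read as a statement about each combination arm, but the evidence behind it is one test of their mean.

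The other planned analyses do not fill the gap. H2 compares the two combination arms with each other, so it says nothing about either against duloxetine. The least square means will show the pattern, but any arm-level comparison with duloxetine made from them would be post hoc. The trial could succeed on H1 and still leave the Section 4.2 question without a controlled answer.

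**Working it through.** **Inputs (Section 9.2).** "With 280 participants and 20% loss to follow-up, we will have 75 evaluable participants in each treatment group": 280 × 0.8 / 3 = 74.7. For the spread, "the estimated standard deviation (SD) for BPI GPS score is 2.2"; with a baseline correlation of 0.5 this gives 2.2 × √(1 − 0.5²) = 1.905, which the plan rounds to 1.9. Alpha is 0.025 two-sided per hypothesis.

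**The plan's own power (noncentral t).**
- Pooled SE = 1.9 × √(1/75 + 1/150) = 0.269. A difference of −1 gives 92.8% power, against 90% stated. The stated figure is slightly conservative, and the gap does not affect this point.
- Arm-versus-arm SE = 1.9 × √(2/75) = 0.310. A difference of −1 gives 83.0% power, against 83% stated, so this one reproduces.

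**Arm effects implied by the plan.** Let s and u be the true effects against duloxetine of the supported and unsupported arms. With equal arms, H1 tests (s + u)/2 and H2 tests s − u. Setting both to −1 gives s = −1.5 and u = −0.5.

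**What pooled success says about the unsupported arm.** The observed pooled difference needed for significance is about −0.61. A supported-arm difference of about −1.21 reaches this with none in the unsupported arm.

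Joint probabilities come from a three-arm simulation: 1,000,000 replicates, 75 per arm, common SD 1.9, variance estimated on 222 df. Success means significant in the hypothesised direction.

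| s / u | H1 | H1 and H2 | H1 without H2 | Unsupported vs duloxetine at 0.025 |
|---|---|---|---|---|
| −1.5 / −0.5 | 92.8% | 77.3% | 15.5% | 26.2% |
| −1 / 0 | 34.8% | 29.0% | 5.8% | 1.2% |
| −1 / −1 | 92.8% | 1.2% | 91.6% | 83.3% |
| 0 / 0 | 1.3% | 0.02% | 1.2% | 1.2% |

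The noncentral t values for the last column are 26.0% at u = −0.5 and 83.0% at u = −1. The row with both effects zero shows that the pooled test keeps its error rate.

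**The gated rule** (pooled H1 first; if significant, each arm against duloxetine at 0.025):
- With u = 0 and s = −1, the unsupported arm is wrongly credited in 1.2% of trials.
- With both effects at −1, the unsupported arm passes gate and test in 82.4% of trials, and by symmetry so does the supported arm. Both pass in 73.3%.

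**Error control within Aim 1.** If both arm nulls hold, the pooled null holds too, and the gate limits the error to 0.025. If only one arm null holds, only one false arm-level rejection is possible, and it is tested at 0.025. H2 keeps its own 0.025.

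**The case against.** The strongest reply is that H1 is a pooled hypothesis by definition. A reader might infer that it claims superiority for both arms separately. The documents do not support that: Section 9.1 defines the comparison as the two groups together, Section 9.2 powers it as 150 versus 75, and the exploratory hypothesis and Section 9.4.7 use the same phrase for the combined arms. Nor is there an error-rate fault in the pooled test. Pairing a pooled contrast with H2 is a legitimate design and matches the two aims in Section 2.1. All of this stands. What remains is wording that can be read for each arm, and a question raised in Section 4.2 that no planned test answers.

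H2 and the least square means also give partial protection. With effects of −1 and 0, most trials that succeed on H1 also succeed on H2 (29.0 of 34.8 percentage points), so the role of support would usually be visible. But a significant H2 leaves open whether the unsupported arm beats duloxetine.

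Three further inferences should be resisted:
- H1 would succeed in 93% of trials with an unsupported effect of zero if the supported effect were −2. That is twice the plan's design difference, and H2 would then be significant in over 99% of trials.
- A reader might fear that the trial will report automated CBT as effective on the pooled result alone. No section plans that claim.
- A reader might say that the scalable form of the intervention goes untested. Section 2.1 ties scalability to the adherence-focused guidance, that is, to the supported arm.

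Finally, the calls are meant to work by increasing engagement with CBT, so a sizeable supported effect beside an unsupported effect of exactly zero is a limiting case. The −1.5 and −0.5 case does not depend on it.

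**Conclusion.** The point holds as a gap between what H1 can be read to say and what is tested. It is not an invalid test. In the case where both of the plan's −1 differences are true, H1 succeeds in 93% of trials, and H1 and H2 together in 77%, while a test of the unsupported arm against duloxetine would have 26% power. The unsupported arm has a real effect of −0.5 in that case, so the issue is missing evidence rather than a false claim. With a supported effect of −1 and no unsupported effect, H1 succeeds in 35% of trials.

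These figures rest on SD 1.9 in every arm, 75 evaluable per arm and equal weights for the two combination arms in the pooled contrast. The plan does not state the contrast weights, or how the contrast combines Weeks 13 and 25. The zero unsupported effect, and pairing the two −1 differences in one scenario, are assumptions made here. The change is worth making because it is cheap and lets the trial answer the Section 4.2 question.

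**What to change.** 1. In Sections 9.1 and 9.4.2 (and where H1 is repeated in Sections 2.1 and 3), word H1 as the average effect of the two combination arms against duloxetine, and state the contrast weights.
2. Keep the pooled test at two-sided 0.025 as the Aim 1 test, and leave H2 unchanged at 0.025.
3. If the pooled test is significant, test each combination arm against duloxetine at two-sided 0.025 from the same mixed model. Make arm-specific claims only for arms that pass; for any other arm, report the Aim 1 result as a pooled average only.

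The cost is plan wording and two extra contrasts. Pooled power is unchanged, and no patients or alpha are added. The real price is a narrower Aim 1 claim when an arm fails: with both true effects at −1, each arm passes in about 82% of trials but both in only about 73%, so about 27% of such trials could not make the claim for both arms.
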